Confidentiality and Privacy:

Participant information collected in this study will comply with the standards for protection of privacy of individually identifiable health information as promulgated in HIPAA and as mandated in Title 45 CFR, Parts 160 and 164. All records will be kept confidential, and the participant's name will not be released at any time. Participant records will not be released to anyone other than responsible regulatory authorities, when requested. In all cases, caution will be exercised to assure the data are treated confidentially and that the participant's privacy is guaranteed.

An authorization for use and disclosure of protected health information under the HIPAA Privacy Rule will be obtained from every trial participant before, or at the time of, enrollment. It will be presented to, and signed by, the participant at the same time as the study consent. The investigator is responsible for obtaining participants' (or their legal representatives') authorizations and signature and for explaining the elements of the HIPAA authorization form if necessary.

Data and Safety Monitoring:

The principal investigator will be responsible for the overall monitoring of the data and safety of study participants. The principal investigator will be assisted by other members of the study staff. Routine safety data in the review include SAEs, AEs, discontinuation due to AEs, clinically significant post-drug worsening of neurologic status, EKGs, vital signs, and laboratory assessments.

Reporting of Unanticipated Problems, Adverse Events, or Deviations:

Any unanticipated problems, serious and unexpected adverse events, deviations, or protocol changes will be promptly reported by the principal investigator or designated member of the research team to the IRB and sponsor or appropriate government agency if appropriate.

Adverse event reporting:

All AEs occurring between the times informed consent is obtained and the last study-related procedure is completed as part of the day 365 follow up will be recorded on the appropriate eCRF form. Adverse events may be volunteered by subjects and or solicited at each assessment by the investigator or designee.

Recording should be done in a concise manner using standard, acceptable medical terms. The investigator should make every effort to establish a diagnosis of the event based on the presenting signs, symptoms, and/or clinical information. In such cases, the diagnosis should be documented as the AE/SAE.

Diseases, signs, symptoms, or laboratory abnormalities already existing at enrollment are not considered AEs unless they worsen (i.e. increase in intensity or frequency). Surgical procedures themselves are not AEs – they are therapeutic measures for conditions that require surgery. The condition for which the surgery is required may be an AE. Surgical procedures planned before enrollment and the conditions leading to these measures are not AEs.

If, in the investigator's judgment, a clinically significant worsening from baseline is observed in any laboratory or other testing parameter (e.g. EKG, CBC, BMP), physical examination finding, or vital sign, a corresponding clinical AE should be recorded on the AE pages of the eCRF. If the cause is not known, the abnormal test or finding should be recorded as an AE, using appropriate medical terminology. Actual numeric values of test results should not be reported.

Serious adverse event reporting:

All SAEs occurring between the times informed consent is obtained and the last study-related procedure is completed as part of the day 365 follow up, whether or not deemed drug-related or expected, must be reported by the investigator or qualified designee within 1 working day of first becoming aware of the event. The investigator/qualified designee will enter the required information regarding the SAE into the appropriate module of the eCRF, which will automatically result in distribution of the information to DCRI Safety Surveillance. If the eCRF system is temporarily unavailable, the event, including the investigator-determined causality to study drug, should be reported via a paper back-up SAE form to DCRI Safety Surveillance. Upon return of the availability of the EDF system, the SAE information must be entered into the eCRF.

The investigator is responsible for reporting AE/SAEs to their IRB/ethics committee (EDC) according to local guidelines and/or requirements.

All SAEs will be reviewed for expectedness per the Investigator. Events determined to be related to the investigational drug and unexpected per the investigator will be reported in the expedited manner to the regulatory authorities and participating sites. For SAEs resulting in death or considered life threatening,

reporting should occur no later than 7 days after the event; for unexpected, non-life threatening SAEs, reporting should occur no later than 15 days after the event.

Unanticipated problems reporting:

It is the site investigator's responsibility to report UPs to their IRB/EC and to the data coordinating center. The UP report will include the following information:

- Protocol identifying information: protocol title and number, PI's name, and the IRB/EC project number.
- Detail description of the vent, incident, experience, or outcome.
- Explanation of the basis for determining that the event, incident, experience, or outcomes represents a UP.
- Description of any deviations from protocol or other corrective actions that have been taken or are proposed in response to the UP.

To satisfy the requirement for prompt reporting, UPs will be reported using the following timeline:

- UPs that are SAEs will be reported as per the instructions for SAE reporting outlined above.
- Any other UP will be reported to the IRB/EC and to the DCC as per the IRB/EC's reporting requirements, but no later than 30 days of the investigator becoming aware of the problem.
- All UPs should be reported to appropriate institutional officials (as required by an institution's written reporting procedures).

References:

2. van Asch CJ, Luitse MJ, Rinkel GJ, van der Tweel I, Algra A, Klijn CJ. Incidence, case fatality, and functional outcome of intracerebral haemorrhage over time, according to age, sex, and ethnic origin: a systematic review and meta-analysis. *The Lancet Neurology*. 2010;9(2):167-76.
4. Lloyd J. Heart Disease and Stroke Statistics-2010 Update: A Report From the American Heart Association (vol 121, pg e46, 2010). *Circulation*. 2011;124(16):E425-E.

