1.5 Data Sharing

As a member of the International Stroke Genetic Consortium, Wake Forest collaborates to identify medical, environmental and genetic risk factors and causes of stroke to better care for our patients.

The Ethnic/Racial Variations of Intracerebral Hemorrhage (ERICH) study originally recruited over 3000 cases of spontaneous hemorrhage with equal power among white, black and Hispanic cases. ERICH-Gene will combine additional ICH cases from around the world to maximize the power of our study to identify novel genetic variants across ethnicities. The new goal is to perform centralized genotyping of 5,200 new ICH cases under the ERICH-Gene Study with case harmonization of advanced clinical and neuroimaging phenotypes. These data will be de-identified prior to sharing in accordance with NIH dbGap broad data sharing regulations. De-identified data may be shared for future studies according to NIH road data sharing requirements.

Given the devastating nature of ICH and the data provided, a randomized double blinded, placebo-controlled pilot trial of fingolimod plus best standard of care management versus placebo plus best standard of care management in the treatment of ICH is justified. First, given the long half-life of fingolimod, this study will assess the safety of single dosing of fingolimod to be given to critically ill patients, considering that a large portion of patients with ICH requires a prolonged ICU stay (the rate of nosocomial infections in the ICH patient population is approximately 23.1%⁸², and the incidence of clinically significant bradycardia after the first dose has been reported in 0.5%⁶⁰). Secondly, we will explore the use of T and B cell subsets as biomarkers of drug effect in this critically ill patient population. And finally, we will be evaluating for any differences in clinical outcomes during an extended 365 day period and perihematomal edema on radiographic imaging.

Objectives:

Specific Aim #1: Assess the safety of a single dose of fingolimod in patients who present with ICH.

Hypothesis #1: We hypothesize that there will be no difference in adverse events compared with placebo, as defined by a) drug-related adverse events; b) nosocomial infections; and c) neurologic decline.

Specific Aim #2: Evaluate the use of CD4+ T, CD8+ T, and CD19+ B cells as biomarkers of drug effect in a critically ill ICH population.

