Hypothesis #1: We hypothesize that similar to the effect in multiple sclerosis patients, there will be a decrease in inflammatory cells within 24 hours of drug administration, which will persist over 30 days, as

measured by the following biomarkers: CBC with differential and flow cytometry to measure levels of CD4+ T cells, CD8+ T cells, and CD19+ B cells.

Specific Aim #3: Evaluate for differences in clinical outcomes, including a) mortality and disability at 90 and 180 days, and b) perihematomal edema on standard of care radiographic imaging.

Hypothesis#1: We hypothesize that clinical improvement, as measured by mortality and global disability measures established by the NINDS Common Data Elements for Stroke, will be more evident at 180 days than at 90 days, and outcomes will be no worse compared with placebo.

Hypothesis#2: We hypothesize that the biomarker levels of inflammatory cells will correlate with volumetric measurements of perihematomal edema calculated on standard of care neuroimaging modalities (MRI and CT).

Specific Aim #4: Perform multi-omics characterization regarding the immune response related to ICH. We will collect and store DNA from peripheral whole blood at all assessment time points, with additional samples from CSF, if applicable. Stored blood and CSF samples will be used for DNA methylation and metabolomics evaluated with mass spectrometry.

Methods and Measures:

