- If an EVD is present, the drain output will be collected daily as part of standard of care. On Day 1, 3, 5, 7, 10, and 14 after placement, 5 cc at each time point will be collected and 4 cc to be sent off for standard of care infectious surveillance and 1 cc to be saved for future multi-omic analysis. The EVD will be removed in a standard fashion based on the clinical and radiographic determination that the participant no longer has hydrocephalus. If a patient undergoes EVD removal if clinically indicated prior to the Day 10 or 14 collection time points, they will not undergo these final CSF draws.
- Each participant will undergo a standard of care Neuroimaging of the brain 24 hrs and 5-7 days, 90 days, 180 days and 365 days after drug administration to assess the stability and resolution of the hemorrhage, follow the perihematomal edema, evaluate for evidence of hydrocephalus, and the development of subsequent brain atrophy that occurs after ICH. There will be a standard of care Neuroimaging on day 14 if the participant is still hospitalized or clinically indicated.
- 72 hours after admission, each participant will undergo a standard of care non-contrast Neuroimaging of the brain to assess the extent of perihematomal edema after drug administration. There will also be a standard of care Neuroimaging at the 30 day follow up to follow the resolution of hematoma and perihematomal edema. All radiographic data will be used to calculate volumetric measurements via RAPID protocol to measure hematoma and perihematomal edema volume.
- Each participant will undergo standard of care speech, cognitive, physical, and occupational therapy to be initiated upon admission. At time of discharge, post-ICH reference outcome measures established by the NINDS Common Data Elements for Stroke are to be performed and recorded. These will include interviewer-administered modified Rankin Scale (mRS), patient-reported PROMIS 10, Montreal Cognitive Assessment (MoCA), and the Western Aphasia Battery-Revised. These outcome measures will assess for various aspects of recovery, including physical, emotional, and neurocognitive. These clinical assessments will also be performed and recorded at the time of discharge, and at the 30, 90, 180, and 365 day visits. We will also be collecting each participant's disposition at time of discharge, 30, 90, 180, and 365 days.

III. Adverse events:

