- All radiographic imaging performed (CT and MRI) will undergo volumetric measurement calculations of hematoma and perihematomal volumes via RAPID protocol. These volumes will be correlated with biomarker levels of inflammatory cells and clinical outcome assessments.
- NIHSS at 365 days post-ictus.
- *Interviewer-administered modified Rankin Scale score at 365 days post-ictus.*
- Patient-Reported Outcomes Measurement Information System 10 at 365 days (patient report of physical and neurobehavioral function). As referenced in the ICF, all these outcomes measures will be done in the context of a standard of care visit. If any participant endorses symptoms consistent with depression or are at risk of causing harm to self and others, we will follow the institutional policy regarding making the appropriate referral to their primary physician to address these concerns or appropriate psychiatric referral.
- Montreal Cognitive Assessment (MoCA) at 365 days post-ictus.
- Western Aphasia Battery – Revised (WAB-R) at 365 days post-ictus.
- Mortality at 30 days
- Mortality at 90 days
- All cause mortality within the study period
- Patient disposition: number of home days over 365 days
- Multi-omic analysis of inflammatory phenotypes related to ICH

Analytical Plan:

Randomization:

Randomization of the study participants should occur after the participant has undergone eligibility screening and has been consented if all criteria have been met. Consented participants will be allocated to study groups using fixed allocation randomization and a computer-based random number-generating allocation. Allocation will be equal. The study pharmacist will be the only unblinded member of the study and will provide the appropriate study agent based on the statistician's randomization schema. Enrollment into the open-label arm of fingolimod will not be randomized.

Statistical Analysis:

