- **Aim 3. Evaluate differences in mortality and disability between placebo and treatment groups.** Analyses will provide 1) initial percentages of patients who benefit from intervention, specifically focusing on clinical improvements as measured by items from the NINDS Common Data Elements for Stroke, and will provide 2) estimates of variability and correlations in our sample over time. Additional analyses will explore correlations between biomarkers, or their changes over time, including with the perihematomal edema volume. Though the sample sizes in this pilot trial are quite small, these outcome measures have been used extensively in other studies, and our estimates will be helpful to assess comparability in this context, thus informing sample size calculations for a future trial.
- **Aim 4. Perform future multi-omics characterization regarding the immune response related to ICH.** RNAseq Data Analysis: Alignment of reads will be performed using the STAR sequence aligner,⁸⁴ and gene counts determined using feature Counts software.⁸⁵ Differential gene expression (DEG) will be analyzed using DESeq2 software.⁸⁶ All experimental conditions will be prepared in the same experiment, so that the paired-sample analysis can be calculated to detect DEGs at each time point using DESeq2 as described.⁸⁷ Although the primary purpose is to estimate parameters for subsequent power analysis, current analysis will consider Benjamini-Hochberg false discovery rate (FDR) adjusted p<0.05 as significant.⁸⁸ DEGs will be analyzed for significant enrichment of biological pathways and signaling networks using Ingenuity Pathway Analysis (IPA), Causal Network Analysis and Upstream Regulator Tools⁸⁹ and the DAVID software as described.⁹⁰ A parallel analysis to the detection of DEG will be computed on the percent methylation (i.e., estimation of parameters for future power calculations and study design, FDR-adjusted p-values). Further statistical analyses will necessarily rely on data descriptions, and the formal statistical inference (hypothesis testing) will be limited due to the small sample size (n=10).

Human Subjects Protection:

The investigator will ensure that this study is conducted in full conformity with Regulations for the Protection of Human Subjects of Research codified in 45 Code of Federal Regulations [CFR] Part 46, 21 CFR Part 50, 21 CFR Part 56, 21 CFR 312, and/or the International Council on Harmonisation E6.

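### Aim 3 sets out to evaluate differences in perihematomal edema, but no prespecified analysis estimates a fingolimod-placebo difference in edema volume

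*Combined protocol and SAP*

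**What the plan says.** - **Rationale** (closing paragraph before the Objectives): "we will be evaluating for any differences in clinical outcomes during an extended 365 day period and perihematomal edema on radiographic imaging".
- **Objectives, Specific Aim #3:** "Evaluate for differences in clinical outcomes, including a) mortality and disability at 90 and 180 days", followed by "b) perihematomal edema on standard of care radiographic imaging".
- **Aim 3, second hypothesis**, the only one about PHE: "biomarker levels of inflammatory cells will correlate with volumetric measurements of perihematomal edema".
- **Interventions and Interactions, part II:** the scan at 72 hours is taken "to assess the extent of perihematomal edema after drug administration". The 24-hour and 5-7 day scans are also meant to track edema. From day 30 the stated purposes are mainly resolution of hematoma and edema, delayed hydrocephalus and atrophy.
- **Secondary outcome measures:** all CT and MRI "will undergo volumetric measurement calculations of hematoma and perihematomal volumes via RAPID protocol". The use then given is: "These volumes will be correlated with biomarker levels of inflammatory cells and clinical outcome assessments".
- **Statistical Analysis, Aim 3:** the heading reads "Evaluate differences in mortality and disability between placebo and treatment groups". PHE volume appears in this paragraph only within exploratory correlations.

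**The concern.** The aim is about differences, but every stated analysis of PHE volume is about association. A correlation between lymphocyte counts and edema does not show whether fingolimod changed edema. It can arise with no drug effect, for instance if sicker patients differ in both, and it makes no use of the randomisation.

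Smaller edema is part of the protocol's own case for the drug. Section 1.4 cites less PHE in treated rodents and in a small clinical pilot of 3-day dosing. If the plan is followed as written, the trial ends with edema volumes in both randomised arms and no planned estimate of the treatment effect on them. It also ends with no named PHE variance with which to size a later trial.

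Leaving the contrast unspecified carries a second risk. PHE is imaged at up to eight times after enrolment, so a comparison added later could be made at whichever scan looks best.

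**Working it through.** **Step 1. Trace PHE through the plan.** The documents give no PHE effect size, SD or power, so there is no planned figure to reproduce. The check is on the text.

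| Place | Role given to PHE | Arm contrast? |
|---|---|---|
| Rationale before Objectives | Evaluate differences | Implied |
| Specific Aim #3, item b | Evaluate differences | Implied; no comparator or time point named |
| Aim 3, Hypothesis 2 | Correlate with cell biomarkers | No |
| Interventions part II and follow-up visits | Purpose of each scan | No |
| Secondary outcome measures | Measure, then correlate | No |
| Statistical Analysis, Aim 3 | Explore correlations | No; group comparison names mortality and disability |

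The aim sentence does not itself say between arms. That reading comes from Aim 3's first hypothesis, which uses placebo as comparator, and from the heading of the Aim 3 analysis.

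**Step 2. Could a comparison be implied elsewhere?** The t test or Wilcoxon test at two-sided 0.05 is given under Aim 2 for changes in inflammation-related biomarkers, not for imaging volumes. The lymphocyte entry in the secondary outcomes does state a comparison across the three groups; the PHE entry in the same list does not. Where the authors intend a group comparison, they say so.

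**Step 3. Arm size.** The Sample Size section gives 30 in total and 10 open-label patients, without saying whether the 10 are inside the 30. Allocation is equal.
- Inside: (30 - 10)/2 = 10 per randomised arm.
- On top: 30/2 = 15 per randomised arm.

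**Step 4. Precision of the missing contrast.** Let SD be the between-patient SD of PHE volume (or log volume) at the chosen scan. Assume every randomised patient has that scan and no covariate is used. The 95% CI half-width in SD units is t(0.975, 2n - 2) × sqrt(2/n).
- n = 10: 2.101 × 0.447 = 0.94 SD.
- n = 15: 2.048 × 0.365 = 0.75 SD.

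The difference detectable with 80% power at two-sided 0.05, by the normal formula (1.960 + 0.842) × sqrt(2/n), is:
- n = 10: 2.802 × 0.447 = 1.25 SD.
- n = 15: 2.802 × 0.365 = 1.02 SD.

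The t-based values are slightly larger, about 1.3 and 1.06 SD. Power for a 0.8 SD difference is about 43% with 10 per arm and 59% with 15 (normal approximation). The contrast can only be an estimate with an interval.

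**The case against.** The strongest reply is that PHE is analysed. Item b names no comparator, the hypothesis attached to it is correlational, and the outcome list and Aim 3 analysis address that hypothesis. This stands in part: PHE is not ignored, and because the volumes are collected in all participants the gap can still be closed. But the correlation answers the hypothesis and not the aim, and the rationale repeats the intent to look for differences.

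A second reply is proportion. This is a safety and feasibility pilot, PHE is secondary, and the plan admits its samples are small. That is a good reason to report an interval and no powered test. It is not a reason to omit a contrast that the aim sets out to make.

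Three stronger readings may tempt a reader, and the documents do not support them:
- *That the enrolment scan goes unused.* All imaging is to be measured, and the schedule includes imaging at enrolment, so those volumes fall within the planned measurements and correlations. What they lack is a role as covariates in an arm contrast.
- *That an unadjusted contrast would be confounded by hematoma size.* In randomised arms, chance imbalance costs precision; it does not bias the estimate over randomisation.
- *That the trial will give no variance information at all.* The Aim 3 analysis promises estimates of variability in general terms. It does not name PHE.

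**Conclusion.** The point holds: a stated aim, read in its natural sense as fingolimod against placebo, has no prespecified analysis. No part of the plan gives a between-arm estimate, interval, test or analysis time point for PHE volume. To say that the aim can never be answered would go too far, since the data will exist; what is missing is the planned contrast.

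The contrast would be imprecise, with an unadjusted half-width of about 0.94 SD at 10 per arm or 0.75 SD at 15. Both figures assume complete scans, and both widen if patients die or miss the scan. How much covariate adjustment would narrow them depends on a correlation that the documents do not give, so no figure is offered.

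The change should be made. The primary safety aim is unaffected.

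**What to change.** In the secondary outcomes and the Aim 3 analysis:

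1. Add the fingolimod-minus-placebo difference in PHE volume with 95% CI, in randomised patients only. Keep the non-randomised open-label group out of this contrast and describe it separately.
2. Name one early scan as the main time point. The 72-hour scan matches the purpose the protocol gives it. Its clock must be reconciled first: Interventions part II counts from admission, and the schedule table counts from ictus.
3. Report the 24-hour and 5-7 day scans as supportive, and day 30 onward as descriptive of resolution and atrophy.
4. Use ANCOVA, on the log scale if volumes are skewed, adjusted for enrolment-scan hematoma volume, PHE volume or both. State that the adjustment is for precision.
5. Label the result as estimation, and report the PHE SD for use in planning a later trial.
6. State whether the 10 open-label patients are within the 30, so that the expected precision is known.

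Cost: SAP wording, a small analysis and one or two degrees of freedom for covariates. No new scans, measurements or patients are needed.
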